## Step 6: App Registration & Tutorial

### Intervention App

The Register page will appear when intervention participants open the Healthy Detours app for the first time. PBRC staff should assist these participants in entering the following information.

1. User Name: Participants should enter their first and last name
2. Email: Participants should enter the email address that has consistently been provided to PBRC staff. Notably, iPhone users should enter the email address that is associated with their iTunes account.
3. Phone: Participants should enter their cell phone number
4. C-Number: PBRC staff should enter the participant's C-Number (**see page 6**).

Need to add Class Schedule screenshots when they are made available

After intervention participants have registered to Healthy Detours, PBRC staff should give them a tablet to watch the video tutorial: <https://youtu.be/oi9mCUCTmMM>

The link to the YouTube video has been bookmarked on all KB tablets. This video is also available within the Learn to Detour feature of the app.

### Control App

Participants randomized to the control group will be prompted to register for FatSecret when they open the app for the first time. PBRC staff may assist the participants in this registration process.

1. Participants will open the app and select Start Now. They will first be asked to set a goal. Participants may choose whichever goal they want.
2. Participants will input their gender, activity level, weight, height, and date of birth.
3. Participants will sign up with an email address and a password for their account. Participants should be instructed to use the same email address on file with PBRC for this step.
4. Participants will be brought to the home screen of the app.
5. PBRC staff should give control participants the paper-based control tutorial (**Appendix I**) for their reference.

## Step 7: Exit Interview Scheduling

### Six-Week Assessment

An invitation to complete the 6-week interim assessment will be sent to RCT participants via email. Participants who do not complete the surveys within 3 days of invitation will receive an email reminder.

### Posttest Assessment

Participants will receive a reminder email approximately 1 week prior to their previously-scheduled posttest assessment. In addition to the four previously completed surveys, participants will complete the System Usability Scale and the Usage Rating Profile-Intervention (URPI) scale (**Appendix J**) at this meeting. The *Healthy Detours* app will be removed from the participants' phones at this time.

### Participant Compensation

Participants who complete the Posttest Assessment will be informed that their check for \$200 will be requested from LSU Accounts Payable by study staff, and that LSU will mail their checks in approximately 4-6 weeks

Location-based Smartphone Technology to Guide College Students Healthy Choices (Healthy Detours)
Statistical Analysis Plan
NCT02996864
8/16/2016

H1 (Primary): College students randomized to the Healthy Detours app will have greater improvements in their dietary intake quality compared to college students randomized to the control app at 12-week post-test. HEI index is the outcome. Must be calculated from the ASA24 Secondary interest: the nutritional content tracked by the app

H2 (Secondary): College students randomized to the HD app will report greater increases in their physical activity compared to college students randomized to the control app at 12-week post-test.

IPAQ-SF outcomes – standard scoring Secondary: PA (minutes/day) entered into app Phone accelerometry (any additional wearable data from FitBit)

H3 (Secondary): College students randomized to the HD app will report greater improvements in their sleep compared to college students randomized to the control app at 12-week post-test.

PSQI – standard scoring Secondary - Sleep quality (rating of 0-10 of their daily sleep quality) from app Phone accelerometry (any additional wearable data from FitBit)

H4 (Secondary): College students randomized to the HD app will report greater improvements in their quality of life (QOL) compared to college students randomized to the control app at 12-week post-test.

SF-12

Additional analyses will (1) evaluate immediate changes in the diet, PA, and sleep measures at 6 weeks; (2) assess mediators at 6-weeks for a mediational analysis on 12-week outcomes; and (3) evaluate app usage data (e.g., number of log-ins, number of “check-ins”, EMA responses for likability and satisfaction with the app).

The analyses are heavily descriptive in nature for this feasibility trial. Means (standard deviations), medians (Interquartile range), distributions, frequencies and percentiles, etc. will be used to characterize the major outcome measures. Tests will be performed as per the design using simple t-tests followed by analysis of covariance to assess the outcome results adjusted for baseline (rather than change from baseline). Multivariate analyses will be conducted to assess the simultaneous direction of changes between the treatment arms. We will test the four outcomes simultaneously and examine the correlation amongst them within treatment arms. Hotelling’s T2 will be used to test the overall mean vector of responses. This analysis will utilize the pre and post measures, but additional analyses will be conducted using generalized least squares regression (PROC MIXED in SAS ver 9.3 or higher) to account for missing data (drop outs between 6 weeks and 12 weeks).

Characteristics of dropouts will be intensively examined to shed light on potential weaknesses of the app (differential dropout overall or within certain subgroups). The evaluation of the control app will include its impact using the pre-post data. This will provide information on the choice of this app as the relevant control population. As noted, examination of the correlation matrices along with the mean changes will inform whether the variables appear to move similarly in both groups. Thus, one might argue that it not necessarily the best control choice since we would then be measuring the intensity of intervention. Alternatively, very different correlation structures will inform us about how the interventions are working and may provide information on appropriate controls and or strengths and weaknesses.

Utilization data will be examined to understand the acceptability and intensity of interactions with the apps. The penetration of the apps into this young at-risk population is very important in potentially understanding, not only market share, but also potential impact. Complier average causal effect models²¹⁷ will be used to examine the intensity of the intervention app's utilization. Mediation models using the latest bootstrapping methods^{218,219} will be examined to enhance evidence that the changes induced by the treatment effects are consistent with the changes being mediated via the app and the Healthy Detours intervention.

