## Overview

The *Healthy Detours* app will be tested in a 12-week randomized controlled trial (RCT) with 300 college students at Louisiana State University (LSU) during the Fall 2016 and Spring 2017 semesters. RCT enrollment will be split between these two semesters, with approximately 150 students enrolling during each 12-week period. Students will be randomized to either the *Healthy Detours* app or to an active control condition app.

USDA's *SuperTracker* was originally proposed to serve as the control app for the research project. However, only the *SuperTracker* web page is currently functioning, thereby eliminating it as an appropriate control condition for the *Healthy Detours* app.

The research team agreed on the following criteria for the control app:

- Must be publically available at no cost to the user
- Must be compatible with both Android and iPhone platforms
- Must come from a reputable source
- Must not be an app specifically designed for weight loss; weight monitoring apps may be included

Based on these criteria, *Calorie Counter* by FatSecret was selected as the RCT control condition app.

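### Hotelling's T2 has no defined response vector and no baseline covariate; run on change scores or stacked pre/post values it is valid but usually less powerful than a baseline-adjusted global test

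*SAP*

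**What the plan says.** All the relevant text is in the first paragraph of the SAP's analysis methods. For single outcomes the SAP plans t-tests and then "analysis of covariance to assess the outcome results adjusted for baseline (rather than change from baseline". The next sentence turns to the global comparison: "Multivariate analyses will be conducted to assess the simultaneous direction of changes between the treatment arms". The four outcomes are to be tested together, and Hotelling's T2 "will be used to test the overall mean vector of responses". The SAP adds: "This analysis will utilize the pre and post measures". It mentions no baseline covariate for this test.

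The hypotheses H1 to H4 in the SAP identify the four domains: HEI from the ASA24, the IPAQ-SF, the PSQI and the SF-12. They do not say which IPAQ-SF or SF-12 score enters the vector.

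The same paragraph sets the context: "The analyses are heavily descriptive in nature for this feasibility trial".

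**The concern.** At least three tests fit this wording:

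- T2 on four change scores.
- T2 on an eight-element vector of baseline and 12-week values.
- A comparison of 12-week values adjusted for baseline.

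Standard T2 takes no covariates, so an analyst who follows the text literally would run one of the first two. Neither uses the baselines as efficiently as the third, which is the approach the SAP itself chooses for single outcomes. The stacked version also tests baseline differences, so a rejection could reflect chance imbalance rather than the app.

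Two things are at stake. One is power that could be recovered from data already collected. The other is prespecification: the versions can give different p-values on the same data, and the choice stays open until the data are seen. A smaller point is that the stated interest is in direction, while T2 carries no sign.

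**Working it through.** **Inputs.** The Protocol Overview gives the size: "12-week randomized controlled trial (RCT) with 300 college students". Everything else is an assumption, because the documents state no allocation ratio, alpha, effect size, SD, correlation, dropout rate or power. I take n = 150 per arm (1:1, no dropout) and alpha 0.05. There is no power figure in the plan to reproduce.

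**Set-up.** Outcomes are in SD units. R is the 4×4 matrix with a common between-outcome correlation, ρ is the pre-post correlation, and the covariance of (pre, post) is [[1, ρ], [ρ, 1]] ⊗ R. The vector d holds the 12-week effects; the expected baseline difference is zero by randomization. Let q = (n/2) d′R⁻¹d. Power comes from the noncentral F:

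- Baseline-adjusted: F(4, 2n−9), noncentrality q/(1−ρ²) × [1 − 4/(2n−2)].
- Change scores: F(4, 2n−5), noncentrality q/[2(1−ρ)].
- Stacked: F(8, 2n−9), noncentrality q/(1−ρ²).

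Apart from the small degrees-of-freedom factor, the change-score noncentrality is (1+ρ)/2 times the adjusted one. The stacked version keeps the noncentrality but spreads it over eight numerator degrees of freedom instead of four.

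**Worked case.** d = 0.25 on all four outcomes, between-outcome correlation 0.3, ρ = 0.5.

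- q = 75 × 0.0625 × 4/(1 + 3×0.3) = 9.87.
- Adjusted: 9.87/0.75 × (1 − 4/298) = 12.98 on F(4, 291), power 83.0%.
- Change: 9.87/1 = 9.87 on F(4, 295), power 70.1%.
- Stacked: 9.87/0.75 = 13.16 on F(8, 291), power 72.0%.

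**Varying ρ, otherwise as above.**

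| ρ | Adjusted | Change | Stacked |
|---|---|---|---|
| 0.2 | 71.5% | 47.5% | 58.8% |
| 0.3 | 74.1% | 53.6% | 61.7% |
| 0.5 | 83.0% | 70.1% | 72.0% |
| 0.7 | 95.2% | 91.5% | 89.6% |
| 0.8 | 99.3% | 98.7% | 97.8% |

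**Other effect sizes.** With 0.4 SD on all four outcomes the change-score loss is 5 points at ρ = 0.3 and 1 point at ρ = 0.5. With 0.1 SD it is 3 to 4 points for ρ from 0.2 to 0.8.

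**Largest loss over all effect sizes, common ρ.** For change scores: 33 points at ρ = 0, 28 at 0.1, 24 at 0.2, 14 at 0.5 and 2 at 0.9. For the stacked vector: 12.8 points at any ρ.

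**Unequal pre-post correlations.** Let B = diag(ρⱼ). The residual covariance is S = R − BRB and the change covariance is S + (B−I)R(B−I)′. In the noncentralities, (n/2) d′(inverse covariance)d replaces the terms in q: S⁻¹ for the stacked and adjusted tests (the latter with the same factor as before), and the inverse change covariance for change scores. Outcomes are in the order HEI, IPAQ-SF, PSQI, SF-12.

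| Pre-post correlations | Between-outcome | Effects (SD) | Adjusted | Change | Change-score loss |
|---|---|---|---|---|---|
| 0.3/0.5/0.6/0.7 | 0.3 | 0.25 on all | 87.2% | 78.5% | 8.7 |
| 0.3/0.5/0.6/0.7 | 0.3 | 0.4/0.1/0.1/0.1 | 83.1% | 63.3% | 19.8 |
| 0.2/0.5/0.6/0.7 | 0.5 | 0.3/0/0/0 | 84.6% | 55.8% | 28.8 |
| 0.2/0.8/0.8/0.8 | 0.5 | 0.4/0.1/0.1/0.1 | 95.9% | 59.2% | 36.7 |

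**Validity.** In 10,000 simulated null trials (150 per arm, between-outcome correlation 0.3, ρ = 0.5) type I error was 4.9% to 5.0% for the three versions. A separate set of 4,000 trials per setting, at ρ = 0.2, 0.5 and 0.8, gave 4.6% to 5.3%.

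**The case against.** The strongest reply is that the loss depends on a reading the SAP never adopts. It states its preference for baseline adjustment in the sentence just before the multivariate one, and using pre and post measures is compatible with a MANCOVA. A reader might infer that the SAP contradicts itself by moving from adjusted outcomes to changes. The text does not support that: H1 is also worded as a change ("will have greater improvements in their dietary intake quality") and is still analysed by ANCOVA, so the word settles nothing. This objection stands. What remains is an incomplete definition with a conditional loss.

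A second reply is that direction can already be read from the planned per-outcome ANCOVAs and mean changes, and that a mixed-model analysis is planned as well. That also stands. That T2 is unsigned is a property of the test and not an error; it is only a reason to report the signed estimates beside it.

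A third reply is that the effect sizes and correlations are all assumed. That is true, and it cuts both ways: the documents neither establish a material loss nor rule out a large one.

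**Conclusion.** The point holds as a low-severity, nearly free improvement. As written, the global test cannot be programmed uniquely. Its two literal forms hold their type I error but normally have less power than the baseline-adjusted form. In the illustrative case the cost is 13 points for change scores and 11 for the stacked vector.

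No single range describes this trial. The change-score loss is near zero at high pre-post correlation and when effects are very small or very large. It can exceed 25 points when pre-post correlations are low or differ between outcomes. The stacked loss was at most about 13 points in the cases computed, and it shrinks only where power is very low or near 100%. All of this assumes 1:1 allocation, complete data, normal outcomes and equal covariance matrices in the arms.

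A reader might go further and infer that the test is invalid, that a fixed loss is built in, or that the primary hypothesis is weakened. None of these follows. Type I error is held, adjusted means would lose nothing and are not excluded by the text, and the H1 t-test and ANCOVA do not depend on T2. Nothing in the SAP is conditional on the global result.

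**What to change.** State in the SAP that the global test is a two-arm MANCOVA of the 12-week outcomes on treatment, with their baselines as covariates. Name the elements of the vector: HEI, one specified IPAQ-SF score, the PSQI global score, and the specified SF-12 score or scores. Without those names a MANCOVA statement would still leave the vector open. If more than one SF-12 score is used, the vector has more than four elements and the degrees of freedom change to match.

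Report the global test beside the signed, baseline-adjusted ANCOVA differences with 95% confidence intervals, with all scales oriented the same way, and read between-arm direction from those. Mean changes can stay as description.

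The cost is one SAP sentence, one model statement and about one residual degree of freedom per baseline covariate. With four covariates the noncentrality falls by 4/298, or about 1%. No new data are needed, since the Protocol's Posttest Assessment section repeats the baseline instruments: "In addition to the four previously completed surveys, participants will complete the System Usability Scale". With a common pre-post correlation, change scores would come out ahead only at about 0.97 or higher.

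### Hotelling's T2 is specified without an unequal-covariance version, although the SAP leaves open both differing correlation structures and differential dropout; if both occur, the pooled test departs modestly from its nominal level.

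*SAP*

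**What the plan says.** The SAP's first analysis paragraph plans univariate tests and then a joint test. On the univariate side, "Tests will be performed as per the design using simple t-tests followed by analysis of covariance". On the joint side, "We will test the four outcomes simultaneously and examine the correlation amongst them within treatment arms", and for the test itself, "T2 will be used to test the overall mean vector of responses". The T2 analysis uses the pre and post measures. A PROC MIXED regression is added to deal with missing data. The SAP does not say whether variances or covariances are pooled, and it gives no alpha.

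The second analysis paragraph compares the arms' correlation matrices. It considers two outcomes. The variables may move alike in both arms, or else "very different correlation structures will inform us about how the interventions are working". Dropouts are to be studied for "differential dropout overall or within certain subgroups".

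The Protocol (Overview) describes a "12-week randomized controlled trial (RCT) with 300 college students" with two arms. It states no allocation ratio, and neither document gives a dropout rate or standard deviations.

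**The concern.** The standard two-sample T2 replaces the two arms' covariance matrices by one pooled matrix. That is harmless if the covariances are equal, and in large samples also if the arms are of equal size. When both differ, the pooled matrix misstates the variance of the mean difference. The test then rejects too often if the smaller arm has the larger generalized variance, and too rarely in the reverse case.

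The SAP makes the between-arm difference in correlation a question for study, yet its only named omnibus test assumes that there is none. T2 also needs all four outcomes at both time points, so in effect it rests on completers, and differential dropout would make those groups unequal. At stake is whether the p-value of the four-outcome test can be taken at face value.

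**Working it through.** **Inputs from the documents.** 300 students, two arms, four outcomes. The documents state no error rate or sample-size calculation, so there is no figure of the plan's own to reproduce.

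**Assumptions.** 5% level; 1:1 allocation (150 per arm); multivariate normal outcomes; a common correlation r among the four outcomes within an arm; completer numbers as listed. On 150 per arm, 135 completers means 10% dropout, 120 means 20%, 105 means 30%, 100 means 33% and 90 means 40%.

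**Formulas**, with d the vector of mean differences, p = 4 and N = n1 + n2.
- Pooled: T2 = d' Sp^-1 d / (1/n1 + 1/n2). Refer T2(N-p-1)/(p(N-2)) to F(p, N-p-1).
- Unequal-covariance: T2u = d' (S1/n1 + S2/n2)^-1 d. Refer T2u(v-p+1)/(vp) to F(p, v-p+1), with v estimated from the two sample covariances.

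**Step 1: equal arms.** The true covariance of d is (S1+S2)/n. The pooled estimate targets (2/n)(S1+S2)/2, which is the same. Simulation at 150/150 and 120/120 gave 5.0-5.2% for every covariance difference tried. Unequal completers with equal covariances gave 4.9-5.1%.

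**Step 2: smaller arm's covariance doubled, 90 vs 135.**
- True variance, in units of the larger arm's: 2/90 + 1/135 = 0.02963.
- Pooled: (89 x 2 + 134)/223 = 1.399; 1.399 x (1/90 + 1/135) = 0.02591.
- Ratio 1.143, so T2 behaves roughly as 1.143 times a chi-square on 4 df.
- The 5% critical value 9.488 becomes 9.488/1.143 = 8.30, and the tail area is exp(-4.15) x (1 + 4.15) = 8.1%.

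For 105 vs 135 the true variance is 2/105 + 1/135 = 0.02646. The pooled value is (104 x 2 + 134)/238 x (1/105 + 1/135) = 0.02433. The ratio is 1.087, the cut-off 8.73 and the tail area 6.8%.

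**Step 3: correlations differ, SDs equal.** With a common correlation, the covariance has one eigenvalue 1+3r and three equal to 1-r: 1.3 and 0.9 for r = 0.1, 2.8 and 0.4 for r = 0.6. Take 100 completers with r = 0.1 and 135 with r = 0.6.
- First direction: true 1.3/100 + 2.8/135 = 0.03374; pooled (99 x 1.3 + 134 x 2.8)/233 x (1/100 + 1/135) = 0.03765; ratio 0.896.
- Other three: true 0.9/100 + 0.4/135 = 0.01196; pooled (99 x 0.9 + 134 x 0.4)/233 x (1/100 + 1/135) = 0.01066; ratio 1.122.
- Sum of ratios 0.896 + 3 x 1.122 = 4.26 against 4 under a correct variance, so the test is liberal.

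With the correlations swapped the ratios are 1.116 and 0.891. Their sum is 1.116 + 3 x 0.891 = 3.79, so the test is conservative.

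**Step 4: simulated error at nominal 5%.** A range is shown where separate runs differed.

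| Completers (smaller / larger arm) | Difference between arms | Pooled T2 |
|---|---|---|
| 120 / 135 | r 0.1 / 0.6 | about 5.5% |
| 100 / 135 | r 0.1 / 0.6 | 6.3-6.4% |
| 100 / 135 | r 0.6 / 0.1 | 4.0-4.3% |
| 105 / 135 | smaller arm's covariance doubled | 6.8-6.9% |
| 90 / 135 | smaller arm's covariance doubled | 7.9-8.3%, about 8.2% |
| 90 / 135 | smaller arm's covariance halved | 2.9-3.0% |

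The unequal-covariance version stayed between 4.7% and 5.3% in every scenario.

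**Step 5: the t-test.** With unequal completers and only the correlations differing, a pooled t-test stayed at 5.0-5.2%. It moves only if variances differ as well: at 90 vs 135 with a variance ratio of 2, 1.96/sqrt(1.143) = 1.833, which gives 6.7%.

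**Step 6: power.** With equal covariances, r = 0.3 and an assumed shift of 0.4 SD on every outcome, power was 96.0% for both versions at 105/135. At 90/135 it was 94.2% pooled and 94.1% unequal-covariance.

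**The case against.** The strongest reply is that nothing in the plan predicts this problem. The SAP names similar and different correlation structures as alternatives, and it only undertakes to look at dropout. Either condition alone leaves T2 near 5%. The larger figures need 30-40% dropout in one arm against 10% in the other, for which the documents give no basis. The Protocol in fact pays students on completing the posttest (Participant Compensation) and uses an online pre-consent step to limit attrition (Preliminary Enrollment). The covariance-doubling scenarios also leave the correlations unchanged, so only the 0.1 versus 0.6 scenarios model what the SAP mentions. With correlations of 0.2 versus 0.4 the error was at most 5.5% even at 90/135.

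All of that stands, and it limits the size of the point. It does not remove it: the pooled form is the standard meaning of the named test, its level depends on two things the SAP leaves open, and the alternative costs almost nothing.

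A reader might also infer that differing correlations invalidate the t-tests. They do not: correlations among outcomes cannot affect a univariate test, and the SAP mentions no unequal variances. It calls the t-tests simple, without saying pooled or Welch.

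**Conclusion.** The point holds as a low-impact improvement. If completer numbers and covariances both differ by arm, the pooled T2 misses an assumed 5% level. The miss is about half a percentage point at 120/135 and about 1.3 points at 100/135 with correlations 0.1 versus 0.6. It is about 3 points in the most unbalanced doubling scenario, and the error falls below 5% when the imbalance runs the other way. Each figure rests on assumed dropout, covariances, allocation and alpha.

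Two stronger readings are not supported. First, the SAP does not expect differing structures or differential dropout; it allows for them. Second, the primary comparison is not undermined: H1 concerns a single outcome, the HEI, assessed by t-test and then baseline-adjusted ANCOVA. T2 is supportive, in a feasibility trial whose analyses the SAP describes as mainly descriptive. At the more extreme dropout rates assumed here, selection bias would be the larger worry, and changing the covariance estimator does not address it.

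**What to change.** Add one sentence to the SAP's first analysis paragraph: the four-outcome comparison uses the unequal-covariance two-sample T2 with the Krishnamoorthy-Yu (modified Nel-Van der Merwe) degrees of freedom. This costs a few lines of code and, in the power check, no more than about 0.1 percentage point of power when covariances are equal.

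As a secondary safeguard against unequal variances, state that the simple t-tests are Welch tests (4.8-5.2% in every scenario run), and allow an arm-specific covariance (GROUP=arm) in PROC MIXED. No error rates were computed for PROC MIXED or the ANCOVA, so the PROC MIXED suggestion rests on the same reasoning and not on a calculation. The planned examination of dropouts is still needed, because none of these changes deals with selection.

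### The control arm's pre-post change cannot be read as the control app's impact in a trial with no app-free arm, and the companion comparison of correlation matrices has no planned measure of chance

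*SAP*

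**What the plan says.** The protocol (Overview) randomizes 300 students to Healthy Detours or to Calorie Counter by FatSecret, which it describes as an active control. Enrollment is split over two semesters. There is no waitlist, attention-only or app-free arm.

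The SAP's second analysis paragraph says of FatSecret: "The evaluation of the control app will include its impact using the pre-post data". It gives the purpose: "This will provide information on the choice of this app as the relevant control population". It then adds a between-arm reading: "examination of the correlation matrices along with the mean changes will inform whether the variables appear to move similarly in both groups". If they do move similarly, the SAP suggests FatSecret may not be the best control, because the trial would then be measuring how intensive the intervention is. If they do not, "very different correlation structures will inform us about how the interventions are working".

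The matrices come from the first analysis paragraph, which takes the four outcomes together and will "examine the correlation amongst them within treatment arms". Hotelling's T2 is assigned to the mean vector. The mixed model is there for missing data, and bootstrapping is mentioned only for mediation. The same paragraph opens: "The analyses are heavily descriptive in nature for this feasibility trial".

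**The concern.** Impact is a causal word, and here it is attached to a change within one arm. Over a 12-week term, diet, activity, sleep and quality of life may shift for reasons unrelated to any app, and answering the same instruments again may also move scores. Neither document offers a way to separate these from a FatSecret effect, and neither adds a caveat.

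The similar-movement argument has the same gap. It passes from similar movement to a difference of intensity only, which presumes that both apps did something.

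The matrix comparison raises a separate difficulty: with no interval or test, there is nothing against which to judge that two structures are very different.

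At stake is what the trial says about its own comparator. A seasonal trend could be reported as an effect of FatSecret, and chance differences in correlations could be read as differences in mechanism.

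**Working it through.** The documents give no figure to reproduce here: no variance, correlation, trend, dropout rate or allocation ratio. The first step is structural; the others are illustrations under stated assumptions.

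**1. What is identified.** Let c be the FatSecret effect, h the Healthy Detours effect and t the trend, which randomization makes common to the arms.
- Control-arm change = c + t
- Intervention-arm change = h + t
- Difference = h - c

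There are two independent equations and three unknowns. Neither c nor h can be recovered without assuming t, and a larger sample does not help.

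**2. What similar movement can show.** Similar mean changes mean h is close to c. Both apps active (c = h > 0) and both inert (c = h = 0) satisfy this equally. The same holds for the matrices: if both apps change the correlations in the same way, the between-arm difference stays at zero, as it does if neither app acts.

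**3. How readily trend could pass for impact.** The SAP names no test for the control-arm change. Suppose a two-sided 5% paired test were used, with c = 0 and a pre-post correlation of 0.4. In SD units, the standard error of the mean change is sqrt((2 - 2 x 0.4)/n): 0.0894 at n = 150 and 0.1000 at n = 120.

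| Assumed trend (SD) | Significant, n = 150 | Significant, n = 120 |
|---|---|---|
| 0.1 | 20% | 17% |
| 0.2 | 61% | 52% |
| 0.3 | 92% | 85% |

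The 150 per arm assumes 1:1 allocation of the 300; 120 assumes 20% dropout.

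**4. Chance differences between matrices.** Four outcomes give 4 x 3/2 = 6 correlations per arm. Two arms were simulated with identical four-variate normal distributions and a common correlation of 0.2 (20,000 runs).

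| Result under identical matrices | 150 per arm | 120 per arm |
|---|---|---|
| At least one of six differs by more than 0.20 | 35% | 48-49% |
| Two or more | 7% | 13-14% |
| Three or more | 1% | 3% |
| Largest exceeds 0.30 | 4% | 9% |

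For common correlations from 0.4 down to 0, the first row runs from 20% to 41% at 150 and from 31% to 55% at 120.

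**5. Precision of one difference.** On the Fisher-z scale the 95% half-width is 1.96 x sqrt(2/(n - 3)): 0.229 at 150 and 0.256 at 120. If six such unadjusted intervals were shown, at least one would exclude zero by chance in roughly 24-27% of trials.

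**The case against.** The strongest reply is that the SAP claims little. It calls its analyses descriptive, says the evaluation will include the pre-post data rather than rest on them, examines utilization of the apps as well, and hedges its conclusions. That stands, and it limits the point to one of interpretation. It does not make impact a descriptive word, and the SAP does give the reading a purpose, which is to judge the comparator.

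A second reply is that one correlation differing by 0.20 is a weak version of very different structures. This also stands. On a stricter reading, with several pairs differing or one differing by more than 0.30, chance produces the picture much less often (step 4). The remaining gap is that the SAP sets no criterion, so the reader cannot tell which reading will be applied.

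A reader might infer that real differences in correlation would be lost in chance variation, so that the comparison is worthless. The figures do not support that. Suppose an app with a mean effect of 0.3 SD acts on only a share s of one arm, equally on all four outcomes. This adds v = (0.3/s)² x s(1 - s) to each variance and covariance. With change-score correlation (0.24 + v)/(1.2 + v), the value rises from 0.20 to 0.256, 0.319 or 0.385 for s = 50%, 30% or 20%. All six correlations shift together, so the fair yardstick is their average difference, whose null SD is about 0.061 at 150 per arm. The two larger shifts, 0.12 and 0.185, are 2 to 3 of those SDs. A true difference between matrices can be informative.

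A reader might also fault the plan for ignoring dropout, or for not naming the scale of the matrices. The SAP plans mixed-model analyses and says "Characteristics of dropouts will be intensively examined". On scale, its wording leans towards change: "This analysis will utilize the pre and post measures". Neither is part of this point.

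**Conclusion.** The point holds and is minor. That the control-arm change does not identify a FatSecret effect, and that similar movement cannot distinguish two active apps from two inert ones, follows from the two-arm design and rests on no assumed number. That the matrix comparison lacks any measure of sampling error follows from the SAP's text.

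The percentages are illustrations. They depend on assumed arm sizes, normal data, a common correlation of 0.2 and, for step 3, on trend sizes, a pre-post correlation and a significance test that the documents do not give.

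A reader might infer that the trial's main conclusions are compromised. They are not: H1-H4 are randomized between-arm comparisons in which a common trend cancels.

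**What to change.** (1) In the SAP's second analysis paragraph, replace the reference to the control app's impact with wording such as: *12-week change in the control arm, descriptive and not attributable to FatSecret*. State that this change will not be used alone to judge the comparator, and that similar movement in the two arms will not be read as showing that both apps were active.

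(2) Accompany the between-arm comparison of correlation matrices with one global permutation test of equal matrices, standardizing each outcome within arm first. Show bootstrap intervals for the six differences, resampling students within arm, as description. The permutation test is the better lead. In a simulation check (1,500 runs) it rejected equal matrices in 4.2-5.7% of null trials, while simultaneous max-t bootstrap intervals reached 7.1%, and it had more power.

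The cost is a change of wording and one resampling procedure on data already collected. The downside is a weaker claim about the control app, wide intervals (step 5), and low power unless effects are concentrated in a minority of students. Under the responder model above, the permutation test detects the difference in 12%, 42% or 79% of trials at 150 per arm when 50%, 30% or 20% of one arm respond (10%, 35% or 67% at 120). A non-significant result should therefore not be taken as evidence that the matrices are equal.
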